5.3 Definition of Baseline

Baseline is defined as the last scheduled observation prior to dosing. In most cases Visit 2 will act as baseline with assessments done on Day 1, before dose. However, if the required data for a subject is missing for baseline, the previous non-missing evaluation will become the baseline value. If no baseline or previous to baseline evaluations exist then the baseline value will be treated as missing. This definition will be used for all the outcome measures unless otherwise specified.

5.4 Analysis Periods

Analysis periods will be defined using the two randomization dates. The first analysis period (Week 0 to Week16) is defined from the Week 0 visit to the end of Week 16 visit. The second analysis period (>Week 16) is defined as starting after Week 16 to the end of the study.

For the first analysis period (Week 0 to Week 16), summary tables will be displayed by treatment arm A and B. For the second analysis period (>Week 16), summary tables will be displayed by treatment arm A, B1, and B2.

5.5 Changes from the Planned Statistical Analysis in Protocol

There are no significant changes from the planned statistical analysis in the protocol.

The PP Analysis Set definition has been amended to clarify that only those protocol deviations that are deemed significant enough to affect the primary analysis will result in exclusion from this population.

The modified Intention-To-Treat (mITT) Analysis Set has been added as an additional supplementary analysis for Primary Analysis.

Health Outcome Variables

CCI

Clinical Safety and Tolerability

The protocol specified that the clinical safety and tolerability of the transition from EU RPP to M923 as compared with continuous use of EU RPP with regard to AEs will be evaluated with a summary of all TEAEs by treatment arm and by treatment period. However, the number of periods for analysis was redefined to display results

6. STUDY SUBJECTS

6.1 Disposition of Subjects

Subject disposition will be tabulated for each study treatment and all subjects including the number of subjects who are enrolled (i.e., those who have provided informed consent), the number of screen failures as well as the number of subjects who are randomized, treated, complete the study, withdraw with the reason for early withdrawal, and the total count of subjects in each analysis set (as defined in [Section 4](#)). A listing will be presented to describe dates of completion or early withdrawal and the reason for early withdrawal, if applicable, for each subject.

6.2 Demographic and Baseline Characteristics

Demographic characteristics such as age, gender, race, ethnicity, height, weight, and body mass index (BMI) will be summarized by treatment and for all subjects overall. Descriptive statistics will be presented for age, height, weight, and BMI. Frequency counts and percentages will be presented for sex, race, and ethnicity.

Individual subject demographics and baseline characteristics (results from serology screening, pregnancy and follicle-stimulating hormone (FSH) tests, urine alcohol and drug screen, and anti-citrullinated protein antibodies) will be presented in listings. Listings of treatment randomization and study drug administration will also be provided.

6.3 Medical History

Listings of both medical history and tuberculosis history and test will be presented by patient and treatment.

6.4 Prior and Concomitant Medications

Prior medications are defined as any medication discontinued prior to randomization and administration of study drug. Concomitant medications are defined as any medication initiated or continued during the course of the study. Subject listings of all prior and concomitant medications and non-drug therapies will be presented.

All medications will be coded using the latest version of the World Health Organization Drug Dictionary (WHO DD).

6.5 Extent of Exposure

Exposure to study medication will be provided. Exposure will be calculated overall as well as for exposure up to Week 16 and for week 16 onwards. The number of days on study medication (duration of exposure = date of last dose of IP in given time period minus date of first dose of IP +1; if either date is missing, the duration is unknown) will be summarized for each treatment group, presenting mean, median, standard deviation, and range.

Exposure will also be calculated and summarized in terms of patient treatment years.

6.6 Treatment Compliance

Treatment compliance will be calculated as the ratio of the number of injections taken over the total exposure period (determined by a count of Study Drug Administrations) divided by the number of doses that should have been taken over the same period.

The number of doses that should be taken will be calculated based on the week the subject completed or discontinued the study.

If the subject completed/discontinued on an even week (day 1 (Week 0), 2, 4, ..., 48) the number of doses that should be taken over the period is calculated as the week of completion or discontinuation, divided by 2, adding one for the day 1 (Week 0) dose:

$$\frac{\text{Week number}}{2} + 1 \text{ (day 1, Week 0)}$$

If the subject completed/discontinued on an odd week (1, 3, 5, ..., 47) the number of doses that should be taken over the period is calculated as the week of completion or discontinuation, plus one, divided by 2, adding one for the day 1, week 0 dose:

$$\frac{\text{Week number} + 1}{2} + 1 \text{ (day 1, Week 0)}$$

The exposure period for a subject is calculated from the first day the subject took study medication to 13 days after the last day the subject took study medication, inclusive. Study drug compliance will not be calculated for subjects who were distributed but never took study medication.

Treatment compliance will be summarized by study treatment arm (A and B) and subgroup of treatment arm B (B1 and B2) for the safety and PP populations.

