3.	Immunogenicity, as evidenced by the presence of ADAs, following the transition from EU RPP to M923 compared with continuous use of EU RPP assessed as proportion of subjects experiencing seroconversion; titer of ADA levels over time; and neutralizing ADA over time.
INVESTIGATIONAL PRODUCT(S), DOSE, AND MODE OF ADMINISTRATION	
Active Product	M923, a proposed adalimumab biosimilar Dosage form: 40 mg (0.8 mL) prefilled syringe for injection Dosage frequency: 80 mg at Week 0 and then 40 mg every 2 weeks (Q2W) starting at Week 1 Mode of Administration: subcutaneous (SC)
Comparator	Non-US-approved comparator (EU-approved Humira®) referred to as the EU Reference Protein Product Dosage form: 40 mg (0.8 mL) prefilled syringe for injection Dosage frequency: 80 mg at Week 0 and then 40 mg Q2W starting at Week 1 Mode of Administration: SC
SUBJECT SELECTION	
Targeted Accrual	516 subjects planned for randomization 572 subjects actually randomized
Number of Groups/Arms/Cohorts	258 subjects planned to be randomly assigned to Arm A and 258 subjects randomly assigned to Arm B. At Week 16, subjects in Arm B planned to be randomly assigned again to Arms B1 and B2 (up to 129 subjects each)
Inclusion Criteria	
1.	Subjects must be \geq 18 years old at the time of screening
2.	Must be able to understand and communicate with the investigator and comply with the requirements of the study (including administration of SC injections at home) and must give a written, signed, and dated informed consent before any study-related activity. Where relevant, a legal representative will also sign the informed study consent according to local laws and regulations

3. Chronic plaque-type psoriasis diagnosed for at least 6 months before screening
4. Stable plaque-type psoriasis, defined as no significant change in lesional area or severity, for a period of 2 months or more before screening
5. **All countries except Canada:** History of receipt of or candidate for systemic therapy or phototherapy with active plaque-like psoriasis despite topical therapy.
Canada only: History of receipt of or candidate for systemic therapy with active plaque-like psoriasis despite topical therapy.
Canada only: History of phototherapy treatment that was ineffective or phototherapy judged by the treating physician to be inappropriate for the subject
6. Moderate to severe psoriasis at screening and baseline (Visit 2), defined as:
 - a. PASI score ≥ 12
 - b. sPGA score ≥ 3 (based on a scale of 0 to 5)

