8.7.2.1 Injection training

The study staff will train subjects (or a caregiver) on the SC injection procedure. This training should occur at the Baseline Visit. At the Baseline Visit, 2 prefilled syringes are required to be administered. Site staff will show the subject or caregiver how to administer with the first syringe, and the subject (or caregiver) will demonstrate the injection technique by self-administering with the second syringe. The training and performance of self-injection will be documented in the subject's source documents. The Visit at Week 1 may be used for additional training. It is expected that subjects (or caregiver) will self-administer from Week 1 forward. At visits where the subject is to self-inject at the clinic, site staff should observe the injection to ensure it is being performed correctly and to provide retraining as required.

Subjects are to be instructed that used syringes must be placed in a safety container provided by the sponsor. This safety container should be returned to the investigational site for disposal. This training will be documented in the subject's source documents.

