10.7 Procedures for Monitoring Subject Compliance

Subject compliance with the treatment regimen will be monitored by completion of a subject diary detailing the time and date of self-administration/home treatment of M923 or EU RPP.

Subjects receiving less than 18 doses (75% compliance) will be considered non-compliant

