^l Pregnancy testing is only required for female subjects of childbearing potential. Serum test will be done at screening; all other assessments are done on urine.

^m Self-injection training should be provided with the first injection, with subject or caregiver performing the second injection at the first visit. Additional training can be provided with the Week 1 injection, if needed. At all other visits where the injection occurs in clinic, the subject or caregiver should administer the injection and be observed to ensure correct administration.

ⁿ Study drug will be administered in clinic after all required assessments and blood sample collections have been completed at Weeks 0, 1, 17, 19, 21, 25, 27, 37, and 39. Injections will occur at home in-between clinic visits on Weeks 3, 5, 7, 9, 11, 13, 15, 23, 31, 35, 43 and 47. At Weeks 29, 33, 41, and 45, the study drug injections will be completed at home after the assessments are completed at the clinic.

^o When injection occurs in the clinic, subjects should be observed for a minimum of 2 hours in the clinic after injection at Weeks 0, 1, 17, 25, and 37. Subjects should be observed for 30 minutes after injection at Weeks 19, 21, 27, and 39. At Week 48, only return of study drug will occur.

^p The investigator or a qualified designee will evaluate the current injection sites 30 minutes (\pm 10 minutes) after study drug administration in the clinic at Weeks 0, 1, 17, 19, 21, 25, 27, 37, and 39. They should also evaluate any immediately prior injection site at each subsequent visit as applicable. For injections given at home, injection site reactions will be recorded in the subject diary. There will be no injection at Week 48 (Visit 19), but injection site evaluation for previous injections will occur.

^q The subject should bring the diary at all visits between Weeks 1 and 48. The investigator will review the diary for completeness, request missing information periodically and in a timely manner, photocopy and store the applicable pages in the source documents until the original diary is collected. At Week 25, the subject diary will be collected by the investigator and a new one will be provided until Week 48.

^r Visit windows are \pm 1 day at Visit 3, \pm 3 days for Visits 4-19 and \pm 2 weeks for Visit 20. Reference for visit windows/study day is scheduling based

Table 3
Schedule of Study Procedures and Assessments

Phase	Screening	Double-Blind Period																			Safety Follow-up ^s

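### SAP 6.6 divides injections by doses although Week 0 is two injections and one dose, so full compliance can read 104%; separately, Protocol 10.7's 18 doses is 72% of the 25-dose schedule, not 75%

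*SAP*

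**What the plan says.** SAP 6.6 (Treatment Compliance) sets the ratio as "the number of injections taken over the total exposure period (determined by a count of Study Drug Administrations) divided by the number of doses" that were due over the same period. Doses due come from the week in which the subject finished or left. For an even week the rule is the week number "divided by 2, adding one for the day 1 (Week 0) dose"; for an odd week it is the week number "plus one, divided by 2, adding one for the day 1, week 0 dose". The section then defines the exposure period as running from the day of first intake to 13 days past the day of last intake. The ratio is to be summarised by arm for the safety and PP populations.

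The dosing itself is "80 mg at Week 0 and then 40 mg every 2 weeks (Q2W) starting at Week 1" (Protocol synopsis), supplied as a "40 mg (0.8 mL) prefilled syringe for injection". Protocol 8.7.2.1 states: "At the Baseline Visit, 2 prefilled syringes are required to be administered". The SAP's own schedule (section 15.2, Table 3, footnote m) describes self-injection training "with subject or caregiver performing the second injection at the first visit".

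Protocol 10.7 gives the only compliance figure in either document: "Subjects receiving less than 18 doses (75% compliance) will be considered non-compliant".

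**The concern.** The numerator and denominator of the SAP ratio are in different units. Week 0 contributes two injections to the top and one dose to the bottom, and nothing in SAP 6.6 caps the ratio, adjusts the denominator or says that the two syringes count as one administration. Read as written, complete adherence exceeds 100% and a subject who missed one later dose looks perfect. The excess depends on time in study, so a mean over subjects with different durations mixes different amounts of overstatement.

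Two neighbouring statements also fail to fit together. The percentage attached to 18 doses in Protocol 10.7 does not match the number of doses scheduled. And SAP 6.6 announces one period for both parts of the ratio but then describes two.

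At stake is whether the reported compliance figures mean what they appear to mean, including those for the PP set, which carries the primary equivalence analysis.

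**Working it through.** **The plan's own figure.** Protocol 10.7 equates 18 doses with 75%. This implies 18/0.75 = 24 planned doses, and 18/24 = 75% reproduces.

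**Scheduled doses.** From SAP Table 3, footnote n (the same weeks are in Protocol Table 1):

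- in clinic: Weeks 0, 1, 17, 19, 21, 25, 27, 37, 39 (9);
- at home between visits: Weeks 3, 5, 7, 9, 11, 13, 15, 23, 31, 35, 43, 47 (12);
- at home after a visit: Weeks 29, 33, 41, 45 (4).

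The total is 9 + 12 + 4 = 25 dosing occasions. The SAP formula agrees: Week 48 gives 48/2 + 1 = 25, and Week 47 gives (47 + 1)/2 + 1 = 25. On this base, 18 doses is 18/25 = 72%. A base of 24 results if Week 0 is left out, since the doses at Weeks 1, 3, ..., 47 number (47 − 1)/2 + 1 = 24, but Protocol 10.7 does not say that this is meant.

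**Injections.** Week 0 is 80 mg / 40 mg = 2 syringes, and every later occasion is 1. A completer therefore has 25 + 1 = 26 injections.

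**The ratio as written, with Week 0 counted as two injections.** With n doses due and none missed, the ratio is (n + 1)/n. With one later dose missed it is n/n = 100%, against (n − 1)/n on a dose basis.

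| Last week | Doses due n | Injections if none missed | None missed, as written | One missed, as written | One missed, dose basis |
|---|---|---|---|---|---|
| 1 | 2 | 3 | 150.0% | 100% | 50.0% |
| 8 | 5 | 6 | 120.0% | 100% | 80.0% |
| 16 | 9 | 10 | 111.1% | 100% | 88.9% |
| 25 | 14 | 15 | 107.1% | 100% | 92.9% |
| 47 or 48 | 25 | 26 | 104.0% | 100% | 96.0% |

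**With Week 0 counted as one administration.** A completer scores 25/25 = 100%, and one missed dose reads 24/25 = 96%. No excess remains.

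**With one unit in both parts.** Doses over doses gives 25/25 = 100% and 24/25 = 96.0%. Injections over injections gives 26/26 = 100% and 25/26 = 96.2%. Either is coherent.

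**The end dates.** No injection can fall after the last one taken, so the choice of end date acts only on the denominator. Take a subject whose last dose is at Week 15, with none missed until then, and who leaves at Week 25. Doses taken are 9.

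- Doses due to the leaving week: (25 + 1)/2 + 1 = 14, so 9/14 = 64.3% (as written, 10/14 = 71.4%).
- Doses due to the end of exposure (13 days past Week 15 falls in Week 16): 16/2 + 1 = 9, so 9/9 = 100% (as written, 10/9 = 111.1%).

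For a completer whose last dose is at Week 47, both end dates fall in Week 48 and give 25.

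**The case against.** The strongest objection is that the 104% rests on a data convention that the documents do not show. The numerator comes from a count of Study Drug Administrations, and neither document says whether Week 0 is stored as one record or two. Some text points to one: the footnote to the design schematic in both documents uses injections for dosing occasions, and the diary in Protocol 10.5 asks whether the full dose was given. This stands as a limit on the percentages. It does not rescue the wording, because the section says injections over doses and the training text and footnote m treat Week 0 as two injections.

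Four stronger readings are tempting, and the documents do not support them.

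- A reader might infer that the mismatch lets someone with 17 doses pass the 18-dose rule. That rule is written in doses and does not use the SAP ratio.
- A reader might set 18 against 26 injections and get 69%. That mixes units: 18 doses including Week 0 are 19 injections, and 19/26 = 73.1%.
- A reader might infer that the differing end dates make early leavers look over-compliant. For someone who stops drug and leaves later, running doses due to the later week lowers the ratio, as the Week 15/Week 25 example shows. The overstatement for short stays comes from the Week 0 count alone.
- A reader might infer that the ratio decides membership of the PP set. The Protocol's summary of changes describes the 10.7 criterion in those terms, but the current Protocol 10.7 and 13.2 and SAP 4.2 and 6.7 do not. They define PP by deviations judged individually before unblinding and cite neither this ratio nor a cut-off on it.

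It is also fair that the same formula applies in both arms and that SAP section 5 confines formal testing to the primary outcome.

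**Conclusion.** Wrong as written; severity minor.

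The unit mismatch is in the text. Its size is conditional: if the two Week 0 injections are counted separately, compliance is overstated by one dose in n, which is 4 percentage points for a completer and 11 for someone fully compliant to Week 16, and one missed dose disappears. If Week 0 is one record, the numerical effect is nil and only the wording is at fault.

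The other two points hold under either convention. On the 25-dose schedule, 18 doses is 72%; 75% needs a base of 24 that no text states. And the two end dates in SAP 6.6 can give 64.3% or 100% on a dose basis for the same subject who stopped drug before leaving.

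The consequence is confined to a descriptive compliance summary for the safety and PP sets. The PASI75 comparison, its margins and its confidence intervals do not use the ratio.

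**What to change.** In SAP 6.6:

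- Count dosing occasions in both numerator and denominator, with the two Week 0 syringes as one dose, and say how a Week 0 visit at which only one syringe was given is counted.
- Name one end date and use it for both doses taken and doses due. Ending at the leaving week counts doses after stopping as missed; ending with exposure describes adherence while on drug. The sponsor should say which is intended.

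In Protocol 10.7, or by a clarifying statement in the SAP, reconcile the 18-dose figure and the 75% figure with the 25-dose schedule and state the base. Which cut-off should apply is for the sponsor to settle.

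The cost is wording and a small programming change, with no new data. If Week 0 is currently counted as two, reported compliance for fully compliant completers falls from 104% to 100%; if it is stored as one, their figures do not change. The choice of end date affects mainly subjects who stopped drug before leaving the study.

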8.7.3 Description of Treatment

Subjects will be administered 80 mg of M923 or EU RPP at Week 0 and then 40 mg every 2 weeks (Q2W) starting at Week 1 of the study. Self-injections should occur on the same day (\pm 3 days) each treatment week according to a predetermined randomization schedule with 2 arms indicated as follows:

- Arm A: M923 from Weeks 0 to 48 (n = 258 subjects)
- Arm B: EU RPP from Weeks 0 to 16 (last dose at Week 15); then randomized again at Week 16 into Arms B1 and B2:
 - Arm B1: Continues EU RPP from Weeks 17 through 48 (last dose at Week 47; n = up to 129 subjects)
 - Arm B2: Transition to M923 at Week 17; then to EU RPP at Week 25; and to M923 at Week 37 (last dose at Week 47; n = up to 129 subjects)

At Weeks 0, 1, 17, 19, 21, 25, 27, 37, and 39, injections will be administered in the clinic after all required assessments and blood sample collections have been completed.

All other injections will be administered by the subjects or caregiver at home (but after assessments completed if a planned injection date coincides with a planned visit date [Weeks 29, 33, 41, and 45]). When injection occurs in the clinic, subjects should be observed for 2 hours in the clinic post-injection at Weeks 0, 1, 17, 25, and 37; at Weeks 19, 21, 27, and 39, subjects should be observed for 30 minutes after injection.

At any time during the study, any of the IPs may be interrupted or discontinued at the discretion of the investigator based on his/her evaluation of the subject's condition or safety. No dose modification is permitted for this study.

When injection occurs in the clinic, the investigator or a qualified designee will evaluate the current injection sites 30 minutes (\pm 10 minutes) after study drug administration in the clinic at Weeks 0, 1, 17, 19, 21, 25, 27, 37, and 39.

They should also evaluate immediately prior injection site at each subsequent visit as applicable ([Section 12.10](#)). For injections given at home, injection site reactions will be recorded in the subject diary ([Section 10.5](#)). There will be no injection at Week 48 (Visit 19), but injection site evaluation for previous injections will occur.

Any injection site reactions, regardless of causality, will be recorded on the AE electronic case report form (eCRF). Any concomitant medications, including those used to treat AE(s), will be recorded on the appropriate eCRF.

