9.3 Withdrawal and Discontinuation

Any subject may voluntarily withdraw (ie, reduce the degree of participation in the study) consent for continued participation and data collection. The reason for withdrawal will be recorded on the End of Study eCRF. Assessments to be done at the termination visit (including in cases of withdrawal or discontinuation) are described in [Section 10.6](#) and [Section 20.2](#).

Discontinuation (ie, complete withdrawal from study participation) may be due to dropout (ie, active discontinuation by subject) or loss to follow-up (ie, discontinuation by subject without notice or action). Additionally, the investigator and sponsor have the discretion to discontinue any subject from the study if, in their judgment, continued participation would pose an unacceptable risk for the subject.

Subjects also will be withdrawn from treatment or discontinued from further study participation for the following reasons:

- Failure to achieve at least a PASI 50 response at Week 25
- The subject becomes pregnant. IP exposure will be discontinued. Attempts will be made to follow the subject through completion of the pregnancy and up to 1 year post-delivery, if feasible. The investigator will record a narrative description of the course of the pregnancy and its outcome
- AEs/SAEs that in the investigator or sponsor opinion, poses an unacceptable risk for continued dosing in the subject
- The subject is determined by the sponsor or investigator to be noncompliant with administration of IP, despite evidence of retraining of the subject. The subject will be discontinued from further participation in the study
- Participation in another clinical study involving an IP during the course of the study

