20. SUPPLEMENTS

20.1 Study 911401 Schematic

Figure 1
Study Design for Baxalta Clinical Study 911401

*Injections administered subcutaneously at Weeks 0 and 1, and then every 2 weeks in each arm. Last dose at Week 47.

Subjects in Arm B are randomized again 1:1 at Week 16 into Arms B1 and B2.

D = Day; EU RPP = Reference Protein Product; N = number of subjects; PASI = Psoriasis Area and Severity Index.

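### SAP 6.6 gives two denominators for treatment compliance, and they disagree for subjects who discontinue

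*SAP*

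**What the plan says.** SAP 6.6 takes the number of injections in the exposure period, "divided by the number of doses that should have been taken over the same period". The period runs from the first dose "to 13 days after the last day the subject took study medication, inclusive". Between those two statements the section sets the doses due in another way: "The number of doses that should be taken will be calculated based on the week the subject completed or discontinued the study". For exit at an even week W the count is W/2 + 1. For an odd week it is "the week of completion or discontinuation, plus one, divided by 2, adding one for the day 1, week 0 dose", that is (W + 1)/2 + 1. The result is tabulated by arm for the safety and PP populations.

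The dosing schedule is in the study schematic (Protocol 20.1): "Injections administered subcutaneously at Weeks 0 and 1, and then every 2 weeks in each arm. Last dose at Week 47". Protocol 9.3 lists among its reasons for withdrawal or discontinuation "Failure to achieve at least a PASI 50 response at Week 25", and SAP 2.1 says such subjects leave the study. Week 25 is a dosing week with an on-site injection. For those visits Protocol 8.7.3 says "injections will be administered in the clinic after all required assessments and blood sample collections have been completed", and Protocol 10.3.2 places the PASI before dosing.

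**The concern.** The exposure-period rule is anchored on the last dose and the formulas on study exit. Once a subject leaves at or after the time the next dose falls due, the two can give different denominators. SAP 6.6 does not say which rule governs, nor which date fixes the week of discontinuation. Protocol 10.6 offers discontinued subjects a follow-up visit 5 weeks after the last dose, so the exit date can fall well past the 13-day limit.

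The exit-week formulas also include the dose scheduled in the exit week. That is right for a subject who was dosed that week. It is wrong for one withdrawn at the visit before injection, who is charged a dose that was never going to be given. The Week 25 PASI50 rule creates a foreseeable group of such subjects.

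At stake is a planned table: two programmers following different sentences of SAP 6.6 would report different compliance for the same discontinued subjects.

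**Working it through.** **Inputs.** Dosing occasions: Week 0, then Weeks 1, 3, ..., 47, so 1 + 24 = 25 (Protocol 20.1). Nominal study day of Week w = 7w + 1, which matches the schedule in SAP 15.2 (Week 25 = Day 176). Formulas and exposure period: SAP 6.6. Week 0 is counted as one administration unless stated.

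**Step 1. The plan's completer count.** At Week 48, 48/2 + 1 = 25, equal to the scheduled occasions. The even- and odd-week formulas equal the number of doses scheduled at or before week W for every W from 0 to 48. As a count of scheduled doses they are correct.

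**Step 2. Adherent subject withdrawn before injection at Week 25.**
- Taken: Weeks 0, 1, 3, ..., 23 = 1 + 12 = 13.
- Exit-week formula: (25 + 1)/2 + 1 = 14 due; 13/14 = 92.9%.
- Exposure period: last dose on Day 162; 162 + 13 = Day 175, one day before the Week 25 dose on Day 176. So 13 due; 13/13 = 100%.

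**Step 3. Last dose at Week 9, study exit at Week 16.**
- Taken: Weeks 0, 1, 3, 5, 7, 9 = 6.
- Exit-week formula: 16/2 + 1 = 9 due; 6/9 = 66.7%.
- Exposure period: last dose on Day 64; 64 + 13 = Day 77; the next dose falls on Day 78. So 6 due; 6/6 = 100%.

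**Step 4. How the exit-week result moves with the case.**

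| Case | Taken | Due by exit week | Ratio |
|---|---|---|---|
| Exit before injection at Week 1 | 1 | 2 | 50% |
| Exit before injection at Week 3 | 2 | 3 | 66.7% |
| Exit before injection at Week 17 | 9 | 10 | 90% |
| Exit before injection at Week 47 | 24 | 25 | 96% |
| Last dose Week 23, exit dated 5 weeks later (Week 28) | 13 | 15 | 86.7% |
| Last dose Week 0, exit dated 5 weeks later (Week 5) | 1 | 4 | 25% |

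For exit before injection at any odd week from 3 to 47, the exposure-period rule gives 100%. At Week 1 it also gives 1/2 = 50%, because the Week 1 dose (Day 8) falls within the 13 days after Day 1.

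**Step 5. Sensitivity of the Week 25 figure.** If the Week 25 injection is given, 14/14 = 100%. If the two syringes used at baseline (Protocol 8.7.2.1) count as two injections, the numerator becomes 14 and the ratio 14/14 = 100%; a completer then scores 26/25 = 104%.

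**Step 6. The Protocol 10.7 threshold.** That section equates 18 doses with 75%, which implies 24 doses (18/24 = 75%). On the SAP completer count, 18/25 = 72%. The rule itself is a count of doses, so 6, 13 or 14 doses fall below 18 whichever denominator is used.

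**The case against.** The strongest reply is that the formulas are sound counts of scheduled doses and that the gap is one of definition: the anchor date is not stated. This is largely right. The odd-week formula is not at fault by itself, since the same Week 25 leaver with exit dated Week 26 also gets 26/2 + 1 = 14 due. But the section also says that numerator and denominator cover the same period and defines that period differently, so it contradicts itself.

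It can also be said that 6/9 is a fair score for a subject who stayed on treatment until Week 16 and missed Weeks 11, 13 and 15, and that the exposure-period rule hides such misses. That stands. The Week 9 case shows that the rules disagree, not that 66.7% is wrong, and the fix must keep those missed doses in the denominator.

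The 92.9% is conditional. Assessments precede injection, but no sentence says outright that a PASI50 non-responder receives no injection at Week 25.

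A reader might infer more than the documents support:
- **That early stoppers range from 67% to 100%.** Step 4 shows 50% and 25% in other cases, so 66.7% belongs to particular scenarios and is no floor.
- **That the Week 9 case changes a classification at the 75% cut-off.** Protocol 10.7 works on fewer than 18 doses, and SAP 6.6 sets no threshold on the ratio.
- **That PP membership is affected.** SAP 6.7 does not name the ratio among its examples of reasons for exclusion, and exclusions are decided case by case before unblinding.

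**Conclusion.** The contradiction is real and minor. For discontinued subjects SAP 6.6 supports two answers: 92.9% or 100% for an adherent subject withdrawn before injection at Week 25, and 66.7% or 100% for last dose at Week 9 with exit at Week 16. For Week 48 completers both rules give 25 doses.

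These figures assume nominal visit days and Week 0 counted as one administration; the first also assumes no Week 25 injection. The documents do not say how many subjects will leave at Week 25, so the effect on the arm summaries cannot be sized.

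The consequence is confined to the descriptive compliance table. The ratio does not enter the PASI75 equivalence analysis.

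**What to change.** Rewrite SAP 6.6 with one denominator:

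- Doses due are the scheduled dosing occasions from Week 0 through the date of treatment discontinuation; 25 for completers.
- The occasion at the stop visit is due only if the dose was given at that visit. A Week 25 leaver then scores 13/13 if not dosed and 14/14 if dosed. Leaving out the stop date altogether would not work: a subject injected at Week 17 and stopped that day would score 10/9 = 111%.
- Doses missed while still on treatment remain due. A last dose at Week 9 gives 6/9 if treatment was stopped at Week 16, and 6/6 if it was stopped before Week 11.
- Week 0 counts as one administration in both numerator and denominator.
- Delete the 13-day exposure period from the compliance calculation and keep the SAP 6.5 definition for exposure duration, which has no 13-day extension.

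The text should name the data field that supplies the treatment discontinuation date. While the section is open, the 24 doses implied by Protocol 10.7 and the 25 in SAP 6.6 should be reconciled. The cost is one paragraph of SAP wording and a small programming change.
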